5.1.2 Formulation, Storage and Packaging

Epacadostat will be supplied as an immediate release tablet in two strengths (25 mg, 100 mg) for oral use. The tablets contain the active drug (epacadostat) along with commonly used compendia! excipients (lactose monohydrate, microcrystalline cellulose, povidone, croscarmellose sodium, colloidal silicon dioxide, magnesium stearate).

Once received by a designated staff member at the study site, epacadostat must be handled and stored safely and properly and kept in a secured location to which only the investigator and designated assistants have access to. Upon receipt, epacadostat should be stored according to the instructions specified on the drug labels. In general epacadostat tablets should be stored at ambient conditions (15°C-30°C or 59°F-86°F).

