11.4.1 Epacadostat

Dose reductions/Interruptions - Epacadostat

In some circumstances, it may be necessary to temporarily interrupt both study treatments as a result of AEs that may have an unclear relationship to study drug. If an interruption is necessary both study treatments should be interrupted.

Any interruptions of> 2 weeks or for LFT abnormalities must be discussed with the medical monitor before resuming treatment. Treatment with both study drugs should be withheld for drug-related Grade 4 hematologic toxicities, nonhematological toxicity Grade 3 (including laboratory abnormalities), and severe or life-threatening AEs.

Epacadostat may be dose reduced according to the guidelines and dose levels described in Table 14.

Dosing interruptions may be permitted in the case of medical/surgical events or logistical reasons not related to study therapy (eg, elective surgery, unrelated medical events,

subject vacation, and/or holidays). Subjects will be placed back on study therapy within 3 weeks of the scheduled interruption. The reason for interruption should be documented in the subject's study record.

For patients who do not tolerate the RP2D of epacadostat in combination with pembrolizumab, three dose reductions are permitted (Table 14) in order to allow the patient to continue on study drug. The following guidelines need to be applied and these changes must be recorded on the Dosage Administration Record. Please refer to Table 15 for dose reduction steps and criteria for interruption and re-initiation of epacadostat for drug-related toxicities. Doses held during the study will not be made up. When toxicity that resulted in a dose reduction improves to grade 1 or less, the dose can be re-escalated at the investigators discretion provided there are no other concomitant toxicities.

Table 14 Dose Modification Algorithm for Adverse Events Associated with Epacadostat

Epacadostat Dose Levels	Dose Level 1 (starting dose)	Dose Level -1	Dose Level -2
Actual Dose	100mg bid	50mg bid	25mg bid

Table 15. Dose Modification Guidelines for Epacadostat Related Adverse Effects without Immune Etiology

Toxicity	Grade	Hold	Timing for	Dose for	Discontinue
		Treatment	Treatment	Treatment	Subject (after
		(Y/N)	Restart	Restart	discussion with PI)
Hematologic	1,2,3	No	N/A	N/A	N/A
Toxicity					
	4	Yes	Permanently discontinue treatment	N/A	Permanently discontinue study treatment
Non Hematologic Toxicity	1	No	N/A	N/A	N/A

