Note: Exception to be treated to similar Grade 1 toxicity: -G2 alopecia	2	Consider holding for persistent symptoms	Toxicity resolves to ::;; grade 1 or baseline	Restart at same dose	Toxicity does not resolve within 12 weeks of last dose of treatment
-G2 fatigue	nyestigator agre	ement subjects	Toxicity resolves to ::;; grade 1 or baseline. Subjects with AEs that stabilize at grade 2 (such as neuropathy) may resume treatment upon principal investigator approval. Permanent discontinuation of epacadostat in setting of grade 4 toxicities with the exception of grade 4 laboratory abnormalities that are deemed clinically insignificant	Restart at 1 dose level lower	Toxicity does not resolve within 12 weeks of last dose of treatment. Permanent discontinuation should be considered for any severe or life threatening event.

With principal investigator agreement, subjects with a laboratory AE still at grade 2 after 12 weeks may continue treatment in the study only if asymptomatic and controlled.

Adverse events of a potential immunologic etiology or immune-related AEs (irAEs) may be defined as an AE of unknown etiology, associated with drug exposure and consistent with an immune phenomenon. Immune-related AEs may be predicted based on the nature of the compounds, their mechanism of action, and reported experience with immunotherapies that have a similar mechanism of action. Special attention should be paid to AEs that may

be suggestive of potential irAEs. An irAE can occur shortly after the first dose or several months after the last dose of treatment.

If an irAE is suspected, efforts should be made to rule out neoplastic, infectious, metabolic, toxin, or other etiologic causes prior to labeling an AE as an irAE.

Immune-related adverse events may be attributable to epacadostat alone, pembrolizumab alone, or the combination of both agents. If the event is clearly related to one of the agents, follow the instructions specific for that agent. If the event is related to both agents, follow the action taken instructions for both.

Suggested supportive care measures for the management of adverse events with potential immunologic etiology are outlined in Table 16. below. Note that several courses of steroid tapering may be necessary as symptoms may worsen when the steroid dose is decreased.

It may be necessary to perform conditional procedures such as bronchoscopy, endoscopy, or skin photography as part of evaluation of the event.

 Table 16:

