 Dose Modification Guidance Epacodostat and Pembrolizumab.

Immune-related AEs	Toxicity Grade or Conditions (CTCAEv4.0)	Study Medication	Action Taken with Study Medication	irAE Management with Corticosteroid and/or Other Therapies	Monitor and Follow-up
		Pembrolizuma b	Withhold until Grade 0-1	Administer corticosteroids (initial dose of l-2mg/kg	 Monitor participants for signs and symptoms of
Pneumonitis	Grade 2	Epacadostat	Withhold until Grade 0-1 Related: Reduce by 1 dose level. Not Related: Same dose level.	prednisone or equivalent) followed by taper	pneumonitis Evaluate participants with suspected pneumonitis with radiographic imaging and initiate corticosteroid treatment Add prophylactic antibiotics for opportunistic infections

Immune-related AEs	Toxicity Grade or Conditions (CTCAEv4.0)	Study Medication	Action Taken with Study Medication	irAE Management with Corticosteroid and/or Other Therapies	Monitor and Follow-up
	Grade 3 or 4, or recurrent grade 2	Pembrolizuma b Epacadostat or matching placebo	Permanent! y discontinue Permanent! y discontinue		
		Pembrolizuma b	Withhold until Grade 0-1	Administer corticosteroids (initial dose of 1-2mg/kg	Monitor participants for signs and symptoms of
Diarrhea / colitis	Grade 2 or 3	Epacadostat	Withhold until Grade 0-1 Related: Reduce by 1 dose level. Not Related: Same dose level.	prednisone or equivalent) followed by taper	enterocolitis (i.e. diarrhea, abdominal pain, blood or mucus in stool with or without fever) and of bowel perforation (i.e. peritoneal signs and ileus). Participants with::;: Grade 2 diarrhea suspecting colitis should
Grade 4		Pembrolizuma b	Permanent! y discontinue		consider GI consultation and performing endoscopy to rule out colitis.
	Grade 4	Epacadostat	Permanent! y discontinue		

Immune-related AEs	Toxicity Grade or Conditions (CTCAEv4.0)	Study Medication	Action Taken with Study Medication	irAE Management with Corticosteroid and/or Other Therapies	Monitor and Follow-up
					substituted via IV infusion.
		Pembrolizuma b	Withhold until Grade 0-1	• Administer corticosteroids (initial dose of 0.5- lmg/kg	Monitor with liver function tests (consider weekly or more
	Grade 2*		Withhold until Grade 0-1	preantsone or equivalent) followed by taper	rrequently until liver enzyme value returned to baseline or is stable
AST/ ALT Elevation or Increased	AST/ ALT Elevation or	Epacadostat	Related: Reduce by 1 dose level.		
Billiubili			Not Related: Same dose level.		

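### Section 11.4.1 permits three epacadostat dose reductions and cites Table 14, but Table 14 lists only two levels below the starting dose, so a third successive one-level reduction has no defined dose

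*Combined protocol and SAP*

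**What the plan says.** Section 11.4.1 of the combined protocol and SAP makes Table 14 the source of the dose levels: "Epacadostat may be dose reduced according to the guidelines and dose levels described in Table 14". For patients who do not tolerate the recommended phase II dose in combination with pembrolizumab, it then states that "three dose reductions are permitted (Table 14) in order to allow the patient to continue on study drug".

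Table 14 follows in the same section. It has three dose columns: Dose Level 1, marked as the starting dose (100 mg bid), Dose Level -1 (50 mg bid) and Dose Level -2 (25 mg bid). There is no Dose Level -3 there or anywhere else in the document.

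Two further tables say when a reduction applies, and both move one level at a time. Table 15 (toxicity without immune etiology) has the instruction "Restart at 1 dose level lower". Table 16 (immune-related events) has "Reduce by 1 dose level" in many rows for epacadostat-related events.

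The same section allows re-escalation once the toxicity is back to grade 1 or better: "the dose can be re-escalated at the investigators discretion provided there are no other concomitant toxicities".

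**The concern.** The sentence and the table it cites disagree on a count that sites have to apply. The text gives a number of reductions, and the table supplies doses for one fewer.

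The practical difficulty comes at the bottom of the table. Consider a patient at Dose Level -2 with a related event that has resolved and whose row in Table 15 or 16 calls for a one-level reduction. The row says to go one level lower. The text, if two reductions have been used, says one more is permitted. Table 14 offers no level to go to. The document does not say how these three instructions are to be combined. Two such patients could be handled differently, each in a way that can be defended from the text, and it would be hard to say afterwards which of them was a protocol deviation. What is at stake is consistent dosing, safety handling and the classification of deviations.

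**Working it through.** No statistical calculation is involved. The check is a count, followed by a reading of which rows lead to the gap.

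**Inputs**

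| Item | Value | Source |
|---|---|---|
| Reductions stated | 3, citing Table 14 | Section 11.4.1, text |
| Levels listed | 1, -1, -2 (100, 50, 25 mg bid) | Section 11.4.1, Table 14 |
| Size of one reduction | 1 level | Tables 15 and 16 |
| Re-escalation | Allowed, investigator's discretion | Section 11.4.1, text |

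**Step 1: try to reproduce the stated figure.** Reductions available = levels listed - starting level = 3 - 1 = 2. The text states 3. Shortfall = 3 - 2 = 1 level.

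**Step 2: is a column simply missing from the extracted table?** The header row and the dose row each carry three matching entries, and the levels run 1, -1, -2 without a break. Nothing suggests a lost column.

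**Step 3: other ways of reaching three.**
- Counting the starting dose gives 3, but the starting dose is not a reduction.
- Counting discontinuation as the third step fails, because the sentence says the reductions exist so that the patient can stay on the drug.
- Counting events across a re-escalation does work. On the path 100 to 50, back up to 100, then 100 to 50 and 50 to 25, there are three downward steps, and only the two lower levels of Table 14 are used. Without an upward step, the path 100 to 50 to 25 ends after two.
- The supply section does not imply an unlisted level. It says "Epacadostat will be supplied as an immediate release tablet in two strengths (25 mg, 100 mg) for oral use", and the smaller strength equals the single dose at Level -2. This does not settle whether the text or the table is in error.

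The contradiction is therefore confined to a third successive step-down.

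**Step 4: which events lead to the gap?** For a patient already at Dose Level -2:

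| Instruction for epacadostat | Examples | Gap reached? |
|---|---|---|
| Continue or no hold | Table 15: hematologic grade 1 to 3, non-hematologic grade 1. Table 16: rash grade 1 or 2, hypothyroidism grade 2 to 4, hyperthyroidism grade 2 | No |
| Same dose | Table 15: non-hematologic grade 2. Table 16: events not related to epacadostat, and some grade 3 rash | No |
| Permanent discontinuation | Table 15: hematologic grade 4. Table 16: pneumonitis grade 3 or 4 or recurrent grade 2, AST/ALT/bilirubin grade 3 or 4, nephritis grade 3 or 4, colitis grade 4, rash grade 4, other immune-related events grade 4 or recurrent grade 3 | No |
| One level lower | Table 15: the row with that restart instruction. Table 16, if related: e.g. first grade 2 pneumonitis, diarrhea/colitis grade 2 or 3, AST/ALT/bilirubin grade 2 (outside the liver-metastases footnote), nephritis grade 2, grade 3 rash that is severe or needs oral steroids | Yes |

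The grade label of the Table 15 row is damaged in the extracted text, so exactly which non-immune events trigger it has to be inferred. The Table 16 rows are enough to show that the gap exists.

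**Step 5: does another provision close it?** The discontinuation column of Table 15 covers toxicity unresolved after 12 weeks and severe or life-threatening events. The general instructions to Table 16 cover non-resolution, or failure to taper steroids, within 12 weeks. Neither addresses a resolved event when no lower level remains.

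**The case against.** The strongest reply has four parts.

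**The text does not say successive.** It permits three reductions, and the same paragraph permits re-escalation, so three can occur within Table 14. This stands as a limit. A reader might infer that a third reduction can never be carried out, and the document does not support that. It does not remove the contradiction, because the sentence cites Table 14 for the three reductions and does not tie the number to re-escalation. If three was meant as a cap on reduction events over the whole course, the text would need to say so.

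**Most events are not affected.** This also stands. A reader might infer that every patient at the lowest level with a further related event is left without an instruction. Tables 15 and 16 do not support that, since many related events lead to continuing, the same dose or permanent discontinuation.

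**There is general guidance.** Intolerance is a listed reason to end treatment (Sections 9.3 and 13.0). The Table 15 discontinuation decision follows discussion with the principal investigator. Interruptions of more than 2 weeks, or for liver function abnormalities, go to the medical monitor before treatment resumes. So a patient who cannot tolerate the lowest level is not wholly without guidance. None of these provisions says what applies when a one-level reduction is called for at Dose Level -2.

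**Few patients will be involved.** Probably so, in a single-arm study of 30, but the document gives no number of patients needing repeated step-downs. Table 10 reports treatment-related events of grade 3 or higher in 15.2% (phase 2) and 22.2% (phase 1) of patients at 100 mg bid. If those rates applied here, which is an assumption, 30 x 0.152 = 4.6 to 30 x 0.222 = 6.7 patients would have at least one. That is not an estimate of those affected: it counts first events rather than arrivals at Level -2, and it leaves out the grade 2 immune-related events that also call for a reduction.

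**Conclusion.** The inconsistency is real: three reductions stated, two available from the cited table, one level short. It is an internal inconsistency, wrong as written, and not a matter of design choice.

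Its reach is limited to patients already at Dose Level -2 who have a further related event for which Table 15 or Table 16 calls for a one-level reduction. The number of such patients cannot be derived from the document and is probably small.

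A reader might go on to infer that the efficacy conclusion is weakened. It is not: the primary rule in Section 14.1 (6 or more responders among 30) and its error rates do not depend on the count of dose levels. A reader might also infer that the text is wrong and the table right, or the reverse. The document does not show which, and this review takes no position.

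The conclusion assumes that Table 14 was extracted complete, which its matching rows support, and that one reduction means one level, as Tables 15 and 16 say.

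**What to change.** Reconcile the number of permitted reductions in Section 11.4.1 with the levels in Table 14. State whether the number refers to successive step-downs or to reduction events in total, given that re-escalation is allowed. Make the text and Tables 14 to 16 consistent on what applies when a one-level reduction is called for at the lowest listed level. The clinical team must decide the content; no dose or rule is proposed here.

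The cost is one number and one or two sentences in an amendment, with no effect on sample size or analysis. Section 16.3 describes the study as completed. If so, the remaining step is to correct the record and to report whether any patient at Dose Level -2 met such an instruction and how that patient was handled.

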9.0 TREATMENT/INTERVENTION PLAN

9.1 Study drugs

Treatment will be administered on an outpatient basis. Reported adverse events and potential risks are described in section 11.0. Modifications and dose delays due to toxicity are described further in section 11.4. The schedule of evaluations and interventions is described in Section 10.

Patients will be treated with epacadostat (100mg tablet), administered orally in tablet form, twice daily, continuously for the 21 days of each treatment cycle, beginning on day 1. Pembrolizumab 200mg/dose will be administered by intravenous infusion on day 1 of cycle one and every three weeks thereafter (±3 days). Pembrolizumab infusion should be administered in 30 minutes, with a window of -5 and +10 minutes, using an infusion pump.

The treatment period with the combination therapy or pembrolizumab will continue every 21days for up to 35 cycles (approximately 2 years) as long as subjects are receiving benefit from treatment and have not had disease progression or met any criteria for study withdrawal and are tolerating therapy. In the case of a patient benefiting from study therapy who discontinue study treatment after the maximal therapy duration of 2 years and subsequently experience disease progression, re-challenge with study therapy will be permitted.

No additional investigational or commercial agents or therapies other than those described below may be administered with the intent to treat the patient's malignancy

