Immune-related AEs	Toxicity Grade or Conditions (CTCAEv4.0)	Study Medication	Action Taken with Study Medication	irAE Management with Corticosteroid and/or Other Therapies	Monitor and Follow-up
			1 dose level. Not Related: Same dose level.		• If Grade 4 lipase/amylase elevation is asymptomatic and abdominal imaging suggests no pathology, study drug administration dosing may continue with medical monitor approval.
		Pembrolizuma b	Withhold until Grade 0- 1	Based on severity of AE administer corticosteroid	Ensure adequate evaluation to confirm
	Immune-related		Withhold until Grade 0-1	s	etiology or exclude other causes
All Other Immune-related AEs		Epacadostat	Related: Reduce by 1 dose level.		
		Not Related: Same dose level.			
	Grade 4 or recurrent	Pembrolizuma b	Permanent! y discontinue		
	Grade 3	Epacadostat	Permanent! y discontinue		

				irAE	
Immuno volotod	Toxicity Grade or	Cturdu	Action Taken with	Management	Manitarand
Immune-related	Grade or	Study	i aken with	with	Monitor and
AEs	Conditions	Medication	Study	Corticosteroid	Follow-up
	(CTCAEv4.0)		Medication	and/or Other	
	,			Therapies	

General Instructions:

- 1. Corticosteroid taper should be initiated upon AE improving to Grade 1 or less and continue to taper over at least 4 weeks.
- 2. For situations where pembrolizumab and epacadostat have been withheld, pembrolizumab and epacadostat/placebo can be resumed after AE has been reduced to Grade 1 or O and corticosteroid has been tapered. Pembrolizumab and epacadostat/placebo should be permanently discontinued if AE does not resolve within 12 weeks of last dose or corticosteroids cannot be reduced to:S 10 mg prednisone or equivalent per day within 12 weeks.
- 3. For severe and life-threatening irAEs, IV corticosteroid should be initiated first followed by oral steroid. Other immunosuppressive treatment should be initiated ifirAEs cannot be controlled by corticosteroids.
- 4. Pembrolizumab should be permanently discontinued if Stevens Johnson Syndrome (SJS) or Toxic Epidermal Necrolysis (TEN) occurs.

NOTES:

- 1. Withhold OR permanently discontinue pembrolizumab + epacadostat at the discretion of the Investigator.
- 2. For participants with Grade 3 or 4 immune-related endocrinopathy where withholding of pembrolizumab and epacadostat is required, pembrolizumab and epacadostat may be resumed when AE resolves to :S Grade 2 and is controlled with hormonal replacement therapy or achieved metabolic control (in case of TIDM)

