11.6.3 CTCAE term (AE description) and grade

The descriptions and grading scales found in the revised NCI Common Terminology Criteria for Adverse Events (CTCAE) version 4.03 will be utilized for AE reporting. All appropriate treatment areas should have access to a copy of the CTCAE version 4.03. A copy of the CTCAE version 4.03 can be downloaded from the CTEP web site http://ctep.cancer.gov/protocolDevelopmenUelectronic_applications/ctc.htm.

11.6.4 Attribution of the AE:

- Definite The AE is clearly related to the study treatment.
- Probable The AE is likely related to the study treatment.
- Possible The AE may be related to the study treatment.
- Unlikely The AE is doubtfully related to the study treatment.
- Unrelated The AE is clearly NOT related to the study treatment.

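### After an immune-related event due to one drug, Section 11.4.1 and Table 16 disagree on what happens to the other drug, and attribution is not graded per drug

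*Combined protocol and SAP*

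**What the plan says.** The text of Section 11.4.1 just before Table 16 starts from the premise that one drug alone may be responsible: "Immune-related adverse events may be attributable to epacadostat alone, pembrolizumab alone, or the combination of both agents". It then gives two rules. For a single cause: "If the event is clearly related to one of the agents, follow the instructions specific for that agent". For a joint cause: "If the event is related to both agents, follow the action taken instructions for both".

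Table 16 has a separate line for each drug. In the hold rows the epacadostat cell reads: "Withhold until Grade 0-1 Related: Reduce by 1 dose level. Not Related: Same dose level". The pembrolizumab cells have no relatedness branch. In the permanent-discontinuation rows both drugs are listed and neither line has a relatedness condition. A note to the table also treats the drugs as a pair: "Withhold OR permanently discontinue pembrolizumab + epacadostat at the discretion of the Investigator".

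Two other passages act on both drugs. Section 9.5 holds both while corticosteroids for related toxicity exceed 10 mg prednisone equivalent daily. The opening of Section 11.4.1 withholds both for drug-related grade 4 hematologic toxicity, grade 3 non-hematologic toxicity, and severe or life-threatening events.

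Section 11.6.4 has five attribution categories, each worded against study treatment as a whole, for example "Definite The AE is clearly related to the study treatment".

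**The concern.** The introductory text makes the action depend on which drug caused the event. The hold rows of Table 16 make it independent of cause and use relatedness only to choose the epacadostat restart dose. Two investigators reading the same section could therefore manage the same patient differently. One would leave the non-causal drug alone, and the other would hold it or stop it for good.

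The stakes are safety management and interpretable exposure data. Each rule rests on a per-drug causal judgement, but the protocol's only attribution scale does not separate the drugs. Dosing records can show which drug was stopped. The stated attribution cannot show why.

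**Working it through.** The plan gives no figure for this point, so the check sets the passages side by side.

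**1. What the introductory rule means.** The word *only* is not in the text. It follows from the contrast between the two sentences: if both lines applied to a single-cause event, the separate sentence for joint causes would do nothing.

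**2. Hold rows.** The epacadostat branch for related and unrelated events appears in these rows:
- pneumonitis grade 2
- diarrhea/colitis grade 2–3
- AST/ALT/bilirubin grade 2
- type 1 diabetes or grade 3–4 hyperglycemia
- hypophysitis grade 2
- hypophysitis grade 3–4 (hold or stop)
- hyperthyroidism grade 3–4 (hold or stop)
- nephritis grade 2
- rash grade 3
- amylase/lipase grade 4
- the hold row for all other immune-related events

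That is 11 rows. Section 11.4.1 defines these events as associated with drug exposure, so an event Not Related to epacadostat is most naturally one due to pembrolizumab. The cell still begins by withholding epacadostat. If the introductory sentence simply meant that the epacadostat line is skipped for such events, the Not Related branch would have almost no use. The two texts conflict here.

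**3. Permanent-discontinuation rows.** These are pneumonitis grade 3–4 or recurrent grade 2, diarrhea/colitis grade 4, AST/ALT/bilirubin grade 3–4, nephritis grade 3–4, rash grade 4, and other events at grade 4 or recurrent grade 3: 6 rows. Nothing in the cells refers to cause. Read alone, the table stops both drugs. Read through the introductory sentence, it stops the causal drug. Both readings are available, so this is an ambiguity.

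**4. What the other passages settle.** Section 9.5 covers the hold rows that give a systemic steroid dose. The lowest is 0.5 mg/kg, which exceeds 10 mg for any patient above 10 / 0.5 = 20 kg. Both drugs are therefore held in those rows, at least until the steroid is reduced. The withholding rule at the opening of 11.4.1 covers the severe rows. What remains is:
- Permanent-discontinuation rows: both passages require a hold. Neither says whether the non-causal drug may resume.
- Hold rows where Table 16 lists no systemic steroid: type 1 diabetes/hyperglycemia, hyperthyroidism, and amylase/lipase. Where these are drug-related and grade 3 or above, the 11.4.1 withholding rule also reaches them. That leaves chiefly new-onset type 1 diabetes below grade 3.
- Hold rows where the steroid is not given a dose (hypophysitis, other events). There, Section 9.5 applies only if the dose exceeds its threshold.

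**5. Attribution.** A per-drug judgement is needed by the introductory sentence, by Table 16 (for epacadostat) and by Appendix B, whose guidance applies to events judged related to pembrolizumab. Section 11.6.4 has no per-drug scale, and no text maps its five categories to Related and Not Related. Section 17.2 asks for the relationship to the treatment or treatments, without a per-drug scale.

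**6. Primary design.** As a side check, the exact binomial rule of 6 or more responses in 30 gives a type I error of 0.0732 at a 10% rate and power of 0.9234 at 30%. These match the stated 0.07 and 92%. None of these figures depends on this point.

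**The case against.** The strongest reply is that the introductory sentence tells the reader which line of Table 16 to use, and a table need not repeat its introduction in every cell. This stands for the permanent-discontinuation rows. A reader might infer that the two texts cannot both be followed there, but the documents support only an ambiguity. The reply fails for the hold rows, because of the Not Related branch.

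A second reply is that Section 9.5 and the opening of 11.4.1 already hold both drugs in most serious cases. This also stands, and it narrows the point to later resumption and a few hold rows. A further sentence in 11.4.1, that any interruption should cover both treatments, adds less because it follows a sentence about events of unclear relationship. The trigger is limited too: immune-related events are defined as of unknown etiology, so few may be clearly due to one drug.

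On attribution, Section 11.6.4 is not the case report form, which the documents do not show. The form may already have per-drug fields. The protocol does not require them.

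Three stronger readings are tempting and not supported:
- *The two drugs always move together in Table 16, contrary to the pembrolizumab-only continuation in Section 9.1.* General instruction 4 names only pembrolizumab for Stevens-Johnson syndrome and toxic epidermal necrolysis, and the ocular text after the table names only epacadostat. Pembrolizumab alone can also arise outside Table 16, for example under the serotonin syndrome procedure, so Section 9.1 does not conflict with the table.
- *The expected frequency can be read from Section 11.* Grade 3 AST increases in 3/117 give 1 − (1 − 3/117)^30 = 54% for at least one in 30 patients. The treatment-related count at grade 3 or above, 2/117, gives 1 − (1 − 2/117)^30 = 40%. Neither estimates events clearly due to one drug.
- *The 6-of-30 decision is affected.* Evaluability does not depend on which rule is followed, and no number of responses gained or lost can be derived.

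**Conclusion.** The concern holds as an internal inconsistency in Section 11.4.1. The introductory rule and the epacadostat hold cells give different actions for an event due to pembrolizumab alone, and the permanent-discontinuation rows leave the fate of the non-causal drug open. The both-drug holds elsewhere limit the practical difference mainly to whether that drug stops permanently or may resume, and to hold rows without systemic steroids. The stated attribution scale does not record the judgement on which these rules depend.

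The number of patients affected cannot be estimated from the documents. The conclusion assumes that Not Related in the epacadostat cells means not related to epacadostat, and that the single-cause and joint-cause sentences are meant as alternatives. The point bears on safety management and attribution records, not on the primary design figures. It takes no view on which management rule is right.

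**What to change.** The sponsor should reconcile the attribution sentences of Section 11.4.1 with Table 16, with the withholding rule at the opening of 11.4.1 and with Section 9.5, so that one rule states for each row what happens to the non-causal drug: hold, permanent stop, or neither, and whether it may resume. The clinical team decides the content.

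In Section 11.6.4, require attribution to be recorded separately for epacadostat and pembrolizumab, and state which of the five categories count as Related in Table 16.

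The cost is a wording amendment and one more field on the adverse-event form, with slightly more data entry. Section 16.3 describes the study as completed. For patients already treated, the equivalent step is to document which reading was applied and to report exposure, and attribution where source records allow, by drug.
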